3.2 Subject Sample

Subjects will be males and females aged 5 years of age and older. A total minimum of 105 subjects will be enrolled with 32-52 of those subjects being febrile. For the purpose of this testing, fever is defined as a core temperature of 99.5°F (37.5°C) or higher.

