4.3 Study Success Evaluation

Accuracy and reliability in welloStationX thermometer readings will be demonstrated if there is close agreement between the welloStationX and the reference device (Welch Allyn SureTemp oral thermometer).

Additionally, agreement values will be referenced against those attained for the prior validation study for the CareGiver thermometer, with agreement values for the welloStationX to be comparable or better to the published data for the Caregiver. This reference is the following:

**Clinical validation of the CAREGIVER[®] non-contact thermometer model
PRO-TF200/PRO-TF300 in febrile and afebrile patients of all ages**

Naja E. [name], Alice Huang & Gary O'Hara MSE

November 2013 Copyright ©2013 Thermomedics[®], Inc.

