The study was a non-randomized, non-blinded single arm design with the subject as his or her own control to evaluate the clinical accuracy of the welloStationX thermometer with respect to that of the standardized Welch Allyn SureTemp oral thermometer in the screening of individuals with fever.

4. Subject Sample

Subjects were 110 males and females aged 5 years of age and older: 33 subjects (30%) were febrile, with fever defined as a core temperature of 99.5°F (37.5°C) or higher; and 77 subjects were afebrile.

Subjects were recruited from amongst non-profit clinical sites and through social media posts for subjects to come to a test site or to be evaluated in his or her own home in the widespread Dallas/Fort Worth area.

Afebrile subjects were compensated with a \$10 gift card and febrile subjects were compensated \$25, the additional amount intended to assist the febrile subject to recovery.

5. Study Procedures

Each subject's temperature was measured three separate times sequentially using the study device, the WelloStationX® (*DUT*) and one time using a new off-the-shelf calibrated Welch Allyn SureTemp oral thermometer with disposable probe covers (the reference thermometer). Each measurement was recorded by a trained technician by following the instructions for use contained in the respective device labeling.

Subject age, gender and race were recorded for each subject, and potential adverse event observation was conducted.

A subject or the subject's guardian was immediately informed if a febrile temperature measurement (99.5°F (37.5°C) or higher) was recorded using the Welch Allyn SureTemp oral thermometer. The subject or guardian will be advised to consider seeking medical attention.

RESULTS

6. Sample Demographics

The sample demographics of gender, age and race are shown below in Tables 1 through 3, respectively, for febrile and afebrile subjects and for subjects overall.

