6.2 Age

Table 2: Subject Age by Febrile Status

Age (years)	Febrile (n=33)	Afebrile (n=77)	Total (n=110)
Mean	44.91	44.73	44.78
Standard deviation	16.92	15.96	16.14

A **t-test for independent samples** revealed no statistically significant difference in mean age between febrile and afebrile subjects: $\mu_a - \mu_b = 0.18$; $t = +0.05$; $df = 108$; $p(\text{two-tailed}) = 0.96$ ($p > 0.05$).

Figure 1 below shows the age distribution of study subjects across the entire range.

[figure not shown]

Figure 1. Age distribution of study subjects.

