7.4 XY Plot and Correlation Coefficient

To further demonstrate the closeness of the relationship between the welloStationX (DUT) and the SureTemp (reference) readings, an XY plot of the two sets of readings was created and is shown in Figure 3 below.

[figure not shown]

Figure 3: XY Plot of welloStationX versus SureTemp for all subjects

$R^2 = 0.80$, indicating a strong linear relationship

8. Clinical Repeatability

Clinical Repeatability was calculated using the pooled standard deviations of the triplicate measurements recorded by the welloStationX.

Table 5 below shows clinical repeatability by febrile status.

Table 5: Clinical repeatability of the welloStationX by febrile status.

Febrile (n=33)	Afebrile (n=77)	All (n=110)
0.13	0.09	0.06

9. Safety Evaluation

There were no observed or reported adverse events for any subject in the study.

DISCUSSION

The results of this clinical study are interpreted both with respect to the study dataset alone and compared to the research data published in the following whitepaper:

Clinical validation of the CAREGIVER® non-contact thermometer model PRO-TF200/PRO-TF300 in febrile and afebrile patients of all ages

Naja E. [name], Alice Huang & Gary O'Hara MSE

November 2013 Copyright ©2013 Thermomedics®, Inc.

This comparison was selected for the following reasons:

1. The reported study clinical data was that which was submitted to the FDA in support of market clearance for the Caregiver Professional Clinical Thermometer (K131771) which is the predicate device in the current submission for K180298.
2. In the reported study, the reference thermometer used was the Welch Allyn SureTemp oral thermometer, the same reference thermometer used in the welloStationX clinical precision study.

There were no notable differences in gender, age or ethnicity by febrile status and age distributions across the spectrum was well represented. Therefore, the subject population was across febrile status was homogenous and the sample overall representative of the intended patient population.

The limits of agreement for the welloStationX are (+0.86, -0.80) which is better than that for the Caregiver study whose limits of agreement was (+0.82, -1.21).

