From the Bland Altman Plot, it is found that only four data points lie just outside the limits of agreement (such that 96.4% of all data points lie within the limits of agreement) which indicates there is a strong agreement between the performance of the welloStationX and the SureTemp and is fewer than the six outliers found in the Caregiver study, most of which also lay further away from the limits of agreement than the four outliers in the welloStationX study.

The limits of agreement did not exceed 0.86 (absolute value) and clinical bias did not exceed 0.03°F for the study population overall. These strong indicators of the close agreement between the performance of the welloStationX and the SureTemp are also superior to those attained in the Caregiver study, where the limits of agreement did not exceed 1.21 (absolute value) and clinical bias did not exceed 0.20 °F for subjects overall.

The highest bias attained was 0.25°F for subjects in the welloStationX febrile subject group, which is still notably lower than the greatest bias attained in the Caregiver study of 0.32°F for subjects in the afebrile group.

The XY Chart further demonstrates the close agreement between the performance of the welloStationX and the SureTemp. The correlation coefficient of 0.80 supports this strong linear relationship.

The notably low clinical repeatability of 0.062 for subjects overall indicates that the absolute difference in repeat measurements taken with the welloStationX is very low and therefore precision across repeated temperature readings is very strong and highly repeatable. Clinical repeatability was comparably high for both the febrile and afebrile subject groups in the welloStationX study, at 0.13 and 0.09, respectively. Each of these clinical repeatability values for the welloStationX thermometer is notably lower than those attained for the Caregiver (0.17 for subjects overall; 0.21 for the febrile subject group and 0.15 for the afebrile subject group).

CONCLUSION

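### The Caregiver benchmark in section 4.3 comes from a study titled as covering all ages while this study covers age five and older, so the reported advantage over the Caregiver cannot be attributed to the device

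*Protocol*

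**What the plan says.** Protocol section 4.3 has two parts. The first asks for close agreement with the SureTemp oral thermometer and gives no numerical limit. The second, introduced as an addition, asks for "agreement values for the welloStationX to be comparable or better to the published data for the Caregiver". The title of the cited source describes a validation of a "non-contact thermometer model PRO-TF200/PRO-TF300 in febrile and afebrile patients of all ages".

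On this study's own population, Protocol section 3.2 says "Subjects will be males and females aged 5 years of age and older", and the indication in section 1.2 has the same lower age limit. The results report (the document supplied as the SAP) describes 110 subjects, 33 of them febrile, with a mean age of 44.78 years and SD 16.14 (Table 2).

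The Discussion gives two reasons for choosing the comparator: it is the predicate device, and its study used the same reference thermometer. It says of the welloStationX limits of +0.86 and -0.80 "which is better than that for the Caregiver study whose limits of agreement was (+0.82, -1.21"; the overall limits and bias "are also superior to those attained in the Caregiver study"; and it calls the repeatability values notably lower. The overall Caregiver figures it uses are for the whole Caregiver sample.

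**The concern.** Children under five can enter only one side of this comparison. If their readings agreed less well with the oral reference, or were biased differently, they would loosen the Caregiver benchmark and leave the welloStationX figures untouched. Some or all of an apparent advantage could then be case mix.

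Neither stated reason for the comparator deals with this. A shared reference thermometer removes one difference between the studies, but not a difference in who was measured. The only age test in the report (section 6.2) compares febrile with afebrile subjects within this study, not the two studies.

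At stake is what can be said against the predicate. Because the close-agreement part of section 4.3 has no number attached, the Caregiver figures are the only numerical yardstick in the success rule.

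**Working it through.** **Inputs.** From the results report: welloStationX overall bias 0.03°F, SD 0.42 (section 7.2) and limits +0.86, -0.80 (section 7.3); Caregiver limits +0.82, -1.21 and unsigned overall bias 0.20°F (Discussion); repeatability 0.13 febrile and 0.09 afebrile (section 8) against Caregiver 0.21, 0.15 and 0.17 overall (Discussion). The share *f* of Caregiver patients under five and their error are not in the documents; every value below is an assumption.

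**1. Reproduce the reported limits.** 0.03 ± 1.96 × 0.42 = +0.853 and -0.793, which matches +0.86 and -0.80 to rounding. The stated limits imply SD = 1.66/3.92 = 0.4235.

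**2. Put both studies on one scale.**
- Half-widths: (0.86 + 0.80)/2 = 0.83 and (0.82 + 1.21)/2 = 1.015. The gap is 0.185°F, or 1 - 0.83/1.015 = 18%.
- Caregiver SD = 2.03/3.92 = 0.518; centre = (0.82 - 1.21)/2 = -0.195.
- The welloStationX interval is narrower, but its upper limit (+0.86) lies slightly further out than the Caregiver's (+0.82).

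**3. Limits of agreement, equal bias in both age groups.** With under-five SD equal to *r* times the older SD, SD_old = 0.518/√(1 - f + f·r²), and the half-width is 1.96 × SD_old.

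| f | r = 1.5: half-width at 5+ | share of 0.185 removed | r needed to remove all of it |
|---|---|---|---|
| 10% | 0.957 | 31% | 2.44 |
| 20% | 0.908 | 58% | 1.86 |
| 33% | 0.854 | 87% | 1.58 |
| 50% | 0.796 | all | 1.41 |

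The last column is √[(0.518² - (1 - f) × 0.4235²)/f] / 0.4235. At r = 1.25, the share removed runs from 28% (f = 20%) to 64% (f = 50%).

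**4. Bias and limits together, f = 33%.** Assume the Caregiver bias is -0.195, as its limits imply, and that its older patients matched the welloStationX (0.03, SD 0.4235).
- Under-five bias: (-0.195 - 0.67 × 0.03)/0.33 = -0.65°F.
- Between-group variance: 0.33 × 0.67 × (0.682)² = 0.103.
- Under-five SD: √[(0.268 - 0.103 - 0.67 × 0.179)/0.33] = 0.37°F.

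The sign is part of the assumption. The report gives the Caregiver bias unsigned, and nothing states which way that study took the difference.

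**5. Repeatability.** The report's overall 0.06 lies below both of its subgroup values, so I pooled them: √[(33 × 0.13² + 77 × 0.09²)/110] = 0.104. For case mix to turn 0.104 into 0.17, the under-five SD would have to be √[(0.17² - (1 - f) × 0.104²)/f] / 0.104 times the older one: about 3.1 at f = 20%, 2.5 at 33% and 2.1 at 50%. By febrile status the values are already 38% lower (0.13 against 0.21) and 40% lower (0.09 against 0.15).

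**The case against.** The strongest reply is that the harm is conjectural. All that is known of the Caregiver age mix is a phrase in a title. Nothing in the documents says that under-fives had larger error, or that they were anything like 20% to 50% of that sample. With a 10% share, the SD ratio needed is extreme. This stands, and it limits the claim: neither the size nor the direction of an age effect can be shown.

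A second reply is that little rests on the comparison. Section 4.3 puts agreement with the SureTemp first, and its Caregiver condition asks only for comparable or better; the superiority language belongs to the Discussion. The Conclusion cites SureTemp agreement and repeatability and does not mention the Caregiver. This also stands, and it lowers the severity. It does not rescue the Discussion, which makes the claims without a caveat.

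A third reply is that matching on age would not make the comparison sound. It would still be an unadjusted contrast between two studies, with no margin, no interval and no stated Caregiver sample size. That is right. For an assumed Caregiver sample of 50 to 200, the 95% interval for the SD ratio (0.82, F distribution, 109 degrees of freedom for this study) runs from 0.64–1.03 to 0.70–0.97, so the difference in spread is borderline even before case mix is considered. This is a further reason to treat the comparison as descriptive.

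A reader might infer that the welloStationX looks better *because* the Caregiver study included young children. The documents do not support that: they hold no Caregiver result by age, and for repeatability the explanation is weak on its own arithmetic.

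**Conclusion.** The concern holds in a limited form. A success condition and several comparative statements set figures from a study titled as covering all ages against a sample aged five and older, and neither document addresses the difference. The reported advantage over the Caregiver therefore cannot be attributed to the device.

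Its possible size depends on unknowns. Under moderate assumptions, case mix could account for most or all of the 0.185°F advantage in half-width; with few under-fives, it could account for little. Explaining the bias gap as well would take a quite specific under-five pattern, and the repeatability gap would need much larger error ratios than the limits do.

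A reader might also infer that the finding of agreement with the SureTemp is undermined. It is not: that evidence is internal to this study and does not use the Caregiver figures. Severity is minor to moderate.

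**What to change.** - **Protocol section 4.3:** take the benchmark from Caregiver patients aged five and older, by febrile status, for bias, limits of agreement and repeatability, where the cited source reports them. If it does not, keep the published figures as a descriptive reference labelled as coming from an all-ages population, not as evidence of superiority.
- **Results report, Discussion:** replace better, superior and notably lower with descriptive wording that gives both sets of figures and states that the comparison is unadjusted, across studies, and between populations with different age ranges. This wording is needed even if the age-restricted figures are found.
- **Results report, Conclusion:** no change on this point.

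The cost is one look-up in the cited source and some rewording, with no new subjects, measurements or analyses of this study's data. The downside is that the claims against the predicate become weaker. If the Caregiver figures become descriptive only, success rests on close agreement with the SureTemp, which has no numerical limit; this change does not fill that gap.

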4.4 Safety Analysis

Safety analysis will be through evaluation of adverse events and comparison of adverse events between use of the welloStationX and the Welch Allyn SureTemp thermometers.

4.5 Handling of Missing Data

Missing data will be handled through multiple imputation methods.

5.0 Consent and Confidentiality

5.1 Informed Consent

The Investigator will be responsible for obtaining from every patient prior to his/her participation in the Study an Informed Consent signed by the patient or legally authorized representative, in accordance with the code of Federal Regulations, Title 21, Part 50.20. The consent form that is used must be the current version and must be approved by both the reviewing IRB and by the Sponsor. Informed consent will be obtained from the patient after a full explanation of the purpose of the study, risks and discomforts involved, potential benefits, etc. have been provided by the Investigator both verbally and in writing. The original signed copy of the informed consent must be maintained in the institution's records, and is patient to inspection by a Sponsor representative.

- Informed consent will be an agreement between the study PI and each subject or the subject's designated caregiver, having the capacity to understand and make an informed decision. Consent will be obtained prior to each potential subject's participation in this clinical trial.
- The subject or the caregiver for each subject participating in this clinical trial will be made aware of the fact that the subject's participation involves research and the intent of the research, the expected duration of participation and a description of the procedures that will be followed.
- The subject or the caregiver for each subject will be made aware of the reasonably expected benefits the subject might receive, as well as any risks or potential discomfort that are involved.
- The subject or the caregiver for each subject will be made aware of alternative procedures that are available to the subject.
- The subject or caregiver for each subject will be made aware that the subject's records will remain confidential, but that the FDA and the IRB has the right to inspect those records.

- The subject or caregiver for each subject will be told that the subject's participation in the clinical trial is voluntary, without force or influence from the investigator or sponsor.
- The subject or caregiver for each subject will be given the name and method of contacting the appropriate person(s) to answer any questions about the research and in the event of research-related injury.

7.2 Privacy and Confidentiality

The sponsor is concerned for the individual patient's privacy; therefore all collected patient data will be treated confidentially, identified only by a patient identification number and investigator initials.

All information provided to the Investigator by the Sponsor, including nonclinical data, protocols, CRFs, and verbal and written information, will be kept strictly confidential and confined to the clinical personnel involved in conducting this study, and no disclosure shall be made except in accordance with any right of publication granted to the Investigator.

APPENDIX B: WELLOSTATIONX LABELING

User Manual provided to site at site initiation visit.

APPENDIX C: Reference Thermometer Labeling

User Manual provided to site at site initiation visit.

APPENDIX D: Study Monitoring

Adverse event reporting including device issue and unanticipated events (reportable to IRB) are included in the Case Report Form. None reported.

Wello Inc.

**CLINICAL RESULTS REPORT FOR THE STUDY:
WELLOSTATIONX DETERMINATION OF
CLINICAL ACCURACY; SEPTEMBER 21, 2018.**

NCT#: NCT03758157

November 28, 2018

Table of Contents

OVERVIEW

1.	Study Background and Purpose	3
2.	Study Device: welloStationX®	3
3.	Study Design	3
4.	Subject Sample	4
5.	Study Procedures	4

RESULTS

6.	Sample Demographics	5
6.1	Gender.....	5
6.2	Age.....	5
6.3	Ethnicity.....	6
7.	Clinical Accuracy	7
7.1	Mean and Standard Deviations	7
7.2	Clinical Bias.....	7
7.3	Limits of Agreement and Bland Althman Plots	7
7.4	XY Plot and Correlation Coefficient.....	8
8.	Clinical Repeatability	9
9.	Safety Evaluation	9
	DISCUSSION	10
	CONCLUSION	11

OVERVIEW

1. Study Background and Purpose

Following initial review of K180298 submitted by Wello, Inc (the Sponsor) for the welloStationX® (the device), the Sponsor received a Deficiency Letter from the FDA on August 2018 requesting provision of appropriate clinical accuracy testing as per standard regulations. Subsequently, Wello, Inc. conducted the requested clinical study to demonstrate clinical accuracy validation of the welloStationX® based on *ISO 80601-2-56 Medical electrical equipment — Part 2-56: Particular requirements for basic safety and essential performance of clinical thermometers for body temperature measurement*.

The primary objective of the study was to determine the Clinical Accuracy of the welloStationX® by:

- evaluating clinical bias with stated uncertainty; and
- determining clinical repeatability.

The results of this clinical study are intended to support the following indications for use: “The welloStationX is a non-contact device intended for use to measure the body temperature of individuals five years of age and older. The welloStationX can be used by medical professionals or laypersons in any public or private indoor facility including home use. The welloStationX has an ambient operating temperature range of 59F – 82.4F (15C – 28C).”

The study lasted approximately four weeks during September and October 2018.

2. Study Device: welloStationX®

The welloStationX® is an automated No-Touch Self-Service Electronic Thermometer designed to provide an accurate temperature reading without the time and exposure of a skilled attendant to the possibility of infection.

The welloStationX® is an electronic thermometer using an infrared sensor of the surface of the forehead adjusting human body skin temperature to oral thermometer without contact.

3. Study Design

The study was a non-randomized, non-blinded single arm design with the subject as his or her own control to evaluate the clinical accuracy of the welloStationX thermometer with respect to that of the standardized Welch Allyn SureTemp oral thermometer in the screening of individuals with fever.

4. Subject Sample

Subjects were 110 males and females aged 5 years of age and older: 33 subjects (30%) were febrile, with fever defined as a core temperature of 99.5°F (37.5°C) or higher; and 77 subjects were afebrile.

Subjects were recruited from amongst non-profit clinical sites and through social media posts for subjects to come to a test site or to be evaluated in his or her own home in the widespread Dallas/Fort Worth area.

Afebrile subjects were compensated with a \$10 gift card and febrile subjects were compensated \$25, the additional amount intended to assist the febrile subject to recovery.

5. Study Procedures

Each subject's temperature was measured three separate times sequentially using the study device, the WelloStationX® (*DUT*) and one time using a new off-the-shelf calibrated Welch Allyn SureTemp oral thermometer with disposable probe covers (the reference thermometer). Each measurement was recorded by a trained technician by following the instructions for use contained in the respective device labeling.

Subject age, gender and race were recorded for each subject, and potential adverse event observation was conducted.

A subject or the subject's guardian was immediately informed if a febrile temperature measurement (99.5°F (37.5°C) or higher) was recorded using the Welch Allyn SureTemp oral thermometer. The subject or guardian will be advised to consider seeking medical attention.

RESULTS

6. Sample Demographics

The sample demographics of gender, age and race are shown below in Tables 1 through 3, respectively, for febrile and afebrile subjects and for subjects overall.

